4.0. Study Objectives

4.1. Primary Study Objective

• To assess the association of hormonal contraceptive use on frequency of pulmonary exacerbations, compared to non-hormonal contraceptive users (primary control) and non-contraceptive users (secondary control).

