The definitions for normal bone, osteopenia, and osteoporosis are based on bone mineral density (BMD) scores. BMD is measured by dual energy X-ray absorptiometry (DXA), which provides both T-scores and Z-scores. These scores are used to define whether a person is categorized as having osteoporosis, osteopenia, or normal bone. According to the World Health Organization (WHO), the T-score is the number of standard deviations (SD) above (+) or below (-) the mean BMD in a young, normal, sex-matched population and is preferred for postmenopausal women. The Z-score is the number of standard deviations (SD) above (+) or below (-) the mean bone density in a normal, sex- and age-matched population and is preferred in females prior to menopause (7). In contrast to WHO criteria, the CFF uses Z-scores for children less than 18 years, considers T- and Z-scores as nearly equivalent for persons between ages 18-30 years, and uses T-score findings for persons with CF ages 30 years and older (8).

Our project is specifically designed to collect more information on these critically important issues by expanding our pilot contraceptive CFFPR study and further assess the safety and efficacy of contraception among patients with CF. With pilot funding from the Society of Family Planning, Drs. [name], [name], and [name] collaborated with two other CF centers to assess feasibility, data completeness, and data accuracy of a pilot contraceptive registry. Having successfully linked women with CF's self-reported information on current and prior contraceptive use with clinical data information obtained from the CFFPR, we are now ready to expand our work to include seven additional CF Centers for a total of ten centers (see Table 2).

The research questions we aim to answer for women with CF, aged 18-45 years in this retrospective study include:

- (1) Are estrogen-containing or progestin-only hormonal contraceptives associated with improved objective pulmonary symptoms compared to women with CF who use non-hormonal methods (control)?
- (2) Are estrogen-containing or progestin-only hormonal contraceptives associated with increased incidence of CFrelated liver disease (as noted with increasing trend of liver enzyme tests), gallbladder disease or thromboembolism?
- (3) Are estrogen-containing or progestin-only hormonal contraceptives associated with increased serum glucose trends (as measured by oral glucose tolerance testing) compared to women using non-hormonal methods?

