3.0. Hypothesis

- Estrogen-containing methods, but not progestin-only methods, reduce the annual rate of pulmonary exacerbations, the microorganisms associated with a more rapid decline in lung function, and improve ppFEV1 (or absolute FEV1) of women with CF when compared to women with CF who use non-hormonal contraception (control group).
- Estrogen-containing oral methods of birth control are associated with higher incidence of gallbladder disease (defined as gallstones, requiring surgery), increased liver function enzyme values, and/or increased incidence of thromboembolism among women with CF.
- Both estrogen-containing and progestin-only hormonal methods improve BMI among women with CF, which is linked to nutritional status.
- The strength of agreement between DXA scan T-scores and CFFPR data about osteoporosis, osteopenia and bone fracture will be "substantial."
- The effectiveness of oral birth control is reduced compared to other methods of hormonal birth control in the presence of CFTR modulator use.
- Hormonal birth control use results in a greater proportion of patients with mucoid *Pseudomonas aeruginosa*, in patients who are *P. aeruginosa* positive, compared to non-hormonal contraceptive users.

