7.7. Sample Size

During the pilot phase, the study team will further discuss the statistical plan to ensure adequate numbers of participants are enrolled in the study. Based on information from participating centers, we expect to enroll approximately 600 women and expect about half of them to be on hormonal contraceptives based on our pilot study. The following table shows the power for detecting different RRs of non-hormonal to hormonal contraceptives in women and baseline proportion of outcome in the non-hormonal contraceptives group.

Table 8: Sample size calculation

	Using Poisson Regression Power to detect a Rate Ratio (hormonal / non-hormonal)
Total Sample Size	RR=0.70
450	0.77
475	0.80
500	0.82
525	0.83
550	0.85
575	0.86

CASE.4.CF Study Protocol

Recent data following the U.S. FDA approval of genetic modulators, show that in this population (mean age 25 years) there are approximately 0.8 PEx/year (13). Using Poisson regression, this study will have 80% power to detect a rate ratio of 0.70 between the progestin-only and combined hormonal groups with 575 enrolled women with CF (assuming alpha 0.05 and an estimated attrition rate of 15%). Although triple therapy has already been FDA approved, we do not anticipate this will affect our retrospective study design since we are evaluating years prior to FDA approval of triple modulator therapy.

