8.0. Methods: Assignment of interventions

8.1. Allocation

Participants will belong to a group based on their choice of contraception. Women with CF will be allocated to hormonal group (intervention), non-hormonal groups (control), and never used contraception.

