9.3. Statistical Methods

Because this is a retrospective cohort study, we are most interested in determining whether this exposure (to hormonal contraception) is associated with our primary outcome (counting the number of pulmonary exacerbations requiring additional IV in a given year) and/or our secondary outcomes (new respiratory microbiology, liver disease/non-cirrhosis, gallstone, requiring surgery/procedure, improved BMI, incidence of VTE, osteoporosis and fragile bone fracture). Women on hormonal contraception will be compared to the primary control group of women on non-hormonal contraception. We will also compare to women on no contraception, as the secondary control group. We will exclude persons with these existing diagnosis at the start of the follow up period for outcome data (January 1, 2010). Within this objective we will be able to calculate incidence rates, relative risks and confidence intervals. We will use Poisson regression to calculate progestin-only and combined hormonal method to non-hormonal method pulmonary exacerbation rate ratios and 95% confidence intervals. This allows for adjustment of follow-up time of each individual.

(Objective 1a): We will evaluate lab values over time (ppFEV1%, serum AST, ALT, alkaline phosphatase) to determine if trends between hormonal contraceptive users and non-hormonal contraceptive users differ. See Table 5 for confounders and covariates that we will use to adjust for the primary and secondary outcomes.

We will model ppFEV1 via generalized estimating equations (GEE), allowing for correlation within a subject, and compare via a fixed effect for exposure. Among women who change or stop contraception, we will estimate and compare within-participant difference in outcomes via the model (if numbers allow). We will censor women who switch method types or become pregnant, and for 6 months post pregnancy, for the primary analysis and subsequently follow them to leverage within-patient data and analyze changes in pulmonary status and contraception. Presence of respiratory microbiology will be estimated longitudinally via GEE with a logit link function. Graphic displays and summary statistics will be used; all *p* values will be two-sided.

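### The hypothesis separates estrogen-containing from progestin-only methods, but the primary objective pools them, and no section says which exacerbation contrast is primary

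*Combined protocol and SAP*

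**What the plan says.** The sections name different contrasts for the same outcome.

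- **Hypothesis (3.0), class-specific:** "Estrogen-containing methods, but not progestin-only methods, reduce the annual rate of pulmonary exacerbations". Research question 1 in section 2.0 also names the classes separately ("Are estrogen-containing or progestin-only hormonal contraceptives associated with improved objective pulmonary symptoms"), and the exposure column of Table 5 lists combined and progestin-only contraception as two items.
- **Primary objective (4.1), pooled:** "To assess the association of hormonal contraceptive use on frequency of pulmonary exacerbations, compared to non-hormonal contraceptive users (primary control").
- **Groups (8.1), pooled:** "Women with CF will be allocated to hormonal group (intervention), non-hormonal groups (control), and never used contraception".
- **Statistical methods (9.3), both:** a pooled sentence, "Women on hormonal contraception will be compared to the primary control group of women on non-hormonal contraception", is followed by a class-specific model, "We will use Poisson regression to calculate progestin-only and combined hormonal method to non-hormonal method pulmonary exacerbation rate ratios and 95% confidence intervals".
- **Power (7.7), two different contrasts:** Table 8 is headed "Power to detect a Rate Ratio (hormonal / non-hormonal"), while the paragraph below it claims "80% power to detect a rate ratio of 0.70 between the progestin-only and combined hormonal groups with 575 enrolled women with CF".

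That makes four contrasts: pooled, combined and progestin-only, each against non-hormonal, and combined against progestin-only. No section designates one as primary or gives a testing order, and none gives the expected split between combined and progestin-only users.

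**The concern.** If the hypothesis holds, the pooled group mixes women with a lowered rate and women with an unchanged one. The pooled rate ratio then moves toward 1 by an amount set by the method mix. It no longer estimates the hypothesised effect, and a null pooled result could sit beside a true estrogen effect.

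With no primary contrast named, any of several ratios could later be presented as the primary result.

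The negative half of the hypothesis has a further problem. A significant combined ratio and a non-significant progestin-only ratio, both against the same control, do not show that the classes differ. That needs the direct class contrast. Section 9.3 does not plan one, although 7.7 claims 80% power for it.

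**Working it through.** **Inputs from the documents.** 0.8 exacerbations per year, alpha 0.05 and 15% attrition (7.7); two-sided tests (9.3); about half of the women on hormonal methods (7.7); rate ratio 0.70 (Table 8); 575 enrolled, so 575 × 0.85 = 488.75, about 489 analysed.

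**Assumptions.** Combined rate ratio 0.70 and progestin-only 1.00, to represent the hypothesis. The combined share of hormonal users, *w*, is not given and is varied. Person-time is not stated in the power calculation; one year is the base case.

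**Formula.** With expected events per control woman λ, SE(ln RR) = √[1/(n₀λ) + 1/(n₁λRR)] and power = Φ(|ln RR|/SE − 1.96).

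**1. Table 8.** The table gives 0.77, 0.80, 0.82, 0.83, 0.85, 0.86 for 450 to 575 women.
- λ = 0.8, equal groups: 0.87 at 450, rising to about 0.93 at 575.
- The same with 15% attrition removed: 0.81 to 0.89.
- λ = 0.62, no attrition removed: 0.77, 0.79, 0.81, 0.83, 0.85, 0.86, within about one point of every row.

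The stated inputs therefore do not reproduce the table. The value 0.62 is a calibration, not a figure from the plan, so both 0.62 and 0.8 are carried forward. The 80% in the text does fit Table 8 at 489 women (0.80 at 475, 0.82 at 500), but the text names another contrast.

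**2. Dilution.** Pooled RR = 0.70*w* + 1.00(1 − *w*) = 1 − 0.3*w*. This is 0.85 at *w* = 0.50, 0.775 at 0.75 and 0.73 at 0.90.

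**3. Worked case, *w* = 0.50, λ = 0.62, 244.4 women per half.**
- Pooled: SE = √[1/151.5 + 1/128.8] = 0.120; |ln 0.85| = 0.1625; 0.1625/0.120 = 1.36; power 0.27.
- Combined only (122.2 women): SE = √[1/151.5 + 1/53.0] = 0.160; |ln 0.70| = 0.3567; 0.3567/0.160 = 2.23; power 0.61.

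**4. Range, 489 analysed, λ = 0.62 to 0.8.**

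| Combined share | Pooled RR | Pooled power | Combined-only power |
|---|---|---|---|
| 50% | 0.85 | 0.27–0.34 | 0.61–0.72 |
| 75% | 0.775 | 0.55–0.65 | 0.73–0.83 |
| 90% | 0.73 | 0.71–0.82 | 0.78–0.87 |

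**5. Longer follow-up, *w* = 0.50, 0.8 per year (pooled, then combined-only).**
- Three years, pure Poisson: 0.76, 0.99.
- Five years, pure Poisson: 0.93, 1.00.
- Five years, negative binomial with dispersion 0.5: 0.53, 0.94.
- Five years, negative binomial with dispersion 1: 0.36, 0.80.

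The gap narrows with longer follow-up only if overdispersion is small.

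**6. Direct class contrast.** Among the roughly 244 hormonal users, RR 0.70 gives power of 0.51–0.62 at a 50% share and 0.44–0.54 at 75%, not 80%.

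**7. Several tests.** Take half the women as controls and a quarter in each class. The two class statistics then correlate at 1/3 through the shared control. By simulation, the chance of at least one false positive at 0.05 is about 9% for the two class tests and about 10% with the pooled test added.

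**The case against.** The strongest reply is that the only sentence specifying a model for exacerbations, in 9.3, is class-specific. Research question 1 and Table 5 also separate the classes. The pooled sentence in 9.3 follows a list of primary and secondary outcomes and can be read as naming the control groups rather than defining a test. This stands in part: the estrogen hypothesis is addressed by a planned analysis, and nobody should conclude that it goes untested. It does not settle which ratio is primary, because 4.1, 8.1 and Table 8 remain pooled.

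A reader might also infer that the pooled test would probably miss a true estrogen effect. The documents do not support that. It needs a combined share near one half and about one person-year per woman, and the plan states neither. Section 2.0 says only that oral pills are among the commonest methods, and pills exist in both classes. Outcome follow-up starts in 2010, so person-time may be several years. Pooled power already exceeds one half at a 75% share, and at a 50% share with three years of pure Poisson follow-up.

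Finally, this is an observational cohort reporting rate ratios with confidence intervals, so a rise from 5% to 9–10% is modest and a fixed testing order is one option among several. That is fair. Naming one primary contrast is still needed for readers to know which result answers the primary question.

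**Conclusion.** The inconsistency is on the page. The hypothesis is class-specific; the objective, grouping and Table 8 are pooled; 9.3 is both; the text of 7.7 powers a further contrast; and none is primary.

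If the hypothesis is true, the pooled comparison has less power than combined versus non-hormonal at every combined share tried. The loss is large at a 50% share and small at 90%. These sizes rest on the assumed rate ratios, 489 women, an even hormonal split and 0.62 to 0.8 events per woman. Whether the pooled test would miss the effect cannot be settled from the documents.

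Two points do not depend on the combined share. The pooled ratio does not estimate the hypothesised effect whenever both classes are present. Separate ratios against a shared control cannot show that the effect is confined to estrogen-containing methods.

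**What to change.** - In 4.1 and 9.3, name combined hormonal versus non-hormonal as the primary contrast, and align the groups in 8.1.
- Make progestin-only versus non-hormonal secondary, or second in a fixed order.
- From the same Poisson model, report the combined-versus-progestin-only rate ratio with its 95% CI, and rest any claim of a class difference on it.
- Keep the pooled hormonal ratio as descriptive.
- In 7.7, relabel Table 8 and its text for the contrast named primary. Restate its power with the assumed class split, person-time and overdispersion written out.

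The cost is wording plus one recalculation. The quoted power will look less favourable because each class has fewer women: on the assumptions above, 0.61–0.72 for combined only at a 50% share. If the hypothesis is wrong and both classes have a rate ratio of 0.70, the pooled test would have been the stronger one (0.80–0.89 at 489 women). That is the price of testing the hypothesis as stated.

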4.2. Secondary Study Objectives/Endpoints

- To assess the association of hormonal contraceptive use on trends in lung function (FEV1) over time, compared to non-hormonal contraceptive users (primary control) and non-contraceptive users (secondary control).
- To assess the association of hormonal contraceptive use on the incidence of venous or arterial thromboembolism.
- To assess the association of hormonal contraceptive use on prevalence of liver dysfunction, defined as gallstones (requiring surgery), hepatic steatosis, hepatic cirrhosis, and/or incidence of increased liver enzyme test values (ALT/GGT). Increased liver enzymes is defined as exceeding upper limit of normal on at least 3 occasions over 12-month period.
- To assess the association of hormonal contraceptive use on serum glucose trends, incidence of insulin resistance or time to CF-related diabetes (requiring insulin treatment).

- To assess association of hormonal contraceptive use on nutritional status through the evaluation of BMI trends.
- To validate bone health information in CFFPR with chart data obtained from one CF center (limited due to need for data use agreements between institutions for EMR data).
- To determine if those using hormonal contraception while using CFTR modulators report higher rates of unintended pregnancy compared to those taking non-hormonal contraception.
- To assess proportion of mucoid *P. aeruginosa*, in patients who are *P. aeruginosa* positive, among hormonal contraception users compared to non-hormonal contraceptive users.

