approved contraceptives has increased significantly since 2001, especially with the FDA-approval of hormonal longacting reversible contraceptive methods. In today's U.S. market, two types of hormonal contraceptives exist: estrogenand-progestin-containing methods (a.k.a. combined hormonal methods) and progestin-only methods. Within the estrogen-containing methods, contraceptive choices include oral pills and non-oral methods, such as the transdermal patch and vaginal ring. Within the progestin-only methods, contraceptive choices include four different hormonal intrauterine devices (IUD), a subdermal implant, a 3-month injectable depo-medroxyprogesterone acetate (DMPA), and progestin-only oral pills

The most recent edition of the national contraceptive guidance for women with medical conditions called the United States Medical Eligibility Criteria for Contraceptive Use (USMEC), was released in 2016 by the Centers for Disease Control and Prevention (CDC), which lists CF as a chronic health condition (6). The USMEC lists all hormonal methods safe to prescribe without restrictions (USMEC = 1), except the 3-month injectable, depot-medroxyprogesterone acetate (DMPA). DMPA is listed as USMEC = 2, in which the advantages of using the method in a woman with CF generally outweighs the theoretical or proven risks because of concerns about DMPA on bone health. Despite these national recommendations, the data for women with CF and hormonal contraception are limited. Potential complications for CF patients include decreased pulmonary function, CF-related diabetes (CFRD), CFLD, increased gallbladder disease, decreased nutritional status, increased venous thromboembolism and poor bone health. There are theoretical concerns that hormonal contraception may adversely impact these complications. Another concern is the reduced efficacy of hormonal contraception, specifically oral contraceptive pills with concomitant use of CFTR modulators.

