- (4) Does hormonal contraceptive use affect nutritional status for women with low body mass index?

- (5) What is the percent agreement between CF Clinic DXA scan T-scores and CFFPR data about osteoporosis, osteopenia and bone fracture?
- (6) Are women who use CFTR modulators and more likely to become pregnant unintentionally while taking hormonal contraception (compared to women on non-hormonal contraception)?
- (7) Does use of hormonal contraception result in a higher proportion of patients with mucoid vs. non-mucoid *Pseudomonas aeruginosa* compared to non-hormonal contraceptive users?

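### The modulator–pregnancy objective sets all hormonal methods against non-hormonal methods, so as planned it tests neither the stated hypothesis (oral versus other hormonal methods) nor the background concern about pills

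*Combined protocol and SAP*

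**What the plan says.** All places are in the combined protocol and SAP.

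- Section 2.0 describes the worry as "reduced efficacy of hormonal contraception, specifically oral contraceptive pills with concomitant use of CFTR modulators".
- Section 3.0 turns it into a hypothesis within hormonal methods: "The effectiveness of oral birth control is reduced compared to other methods of hormonal birth control in the presence of CFTR modulator use".
- Research question 6 (end of section 2.0) asks whether women using modulators are "more likely to become pregnant unintentionally while taking hormonal contraception (compared to women on non-hormonal contraception").
- Section 4.2 sets the matching secondary objective, again hormonal against non-hormonal: "To determine if those using hormonal contraception while using CFTR modulators report higher rates of unintended pregnancy compared to those taking non-hormonal contraception".
- Section 8.1 defines the groups: "Women with CF will be allocated to hormonal group (intervention), non-hormonal groups (control), and never used contraception".
- Section 9.3 gives the general comparison: "Women on hormonal contraception will be compared to the primary control group of women on non-hormonal contraception". Pregnancy is absent from its list of secondary outcomes. It appears only in the censoring rule: "We will censor women who switch method types or become pregnant, and for 6 months post pregnancy, for the primary analysis".
- Table 5 (section 7.5) has no pregnancy outcome. Its exposures are combined and progestin-only contraception.
- Table 10 (section 9.1.3) shows that the survey collects method types with dates or ages of use, modulator start and stop dates, year of each pregnancy, and whether it was planned.

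**The concern.** The hypothesis needs pills and other hormonal methods kept apart. The objective merges them into one group and brings in a comparator that the hypothesis does not mention. Whatever the pooled comparison shows, the hypothesis stays untested.

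Section 2.0 puts pills in both the combined and the progestin-only class, so the exposure split in Table 5 and section 9.3 does not isolate oral methods either. It is also unclear whether the non-hormonal comparator must be on modulators.

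Pills and condoms are the most commonly reported methods according to section 2.0, and the study is meant to inform contraceptive counselling. A pooled result may be read as an answer about pills when it mainly reflects which methods the women happened to use.

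**Working it through.** The documents give no pregnancy rate, effect size or power for this objective, so there is no planned figure to reproduce. The arithmetic below shows how the planned contrast behaves. **Every failure rate is an assumption.**

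**1. The planned contrast**

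Assumed failures per 100 woman-years: pills 7 off and 14 on modulators; other hormonal methods 1; non-hormonal 13 or 5. Let f be the pill share of hormonal use.

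Pooled hormonal rate = f × pill rate + (1 − f) × 1. Pooled RR = pooled rate ÷ non-hormonal rate.

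| f | Pooled rate, doubling | RR vs 13 | RR vs 5 | Pooled rate, no modulator effect | RR vs 13 | RR vs 5 |
|---|---|---|---|---|---|---|
| 0.3 | 0.3×14 + 0.7×1 = 4.9 | 0.38 | 0.98 | 0.3×7 + 0.7×1 = 2.8 | 0.22 | 0.56 |
| 0.5 | 0.5×14 + 0.5×1 = 7.5 | 0.58 | 1.50 | 0.5×7 + 0.5×1 = 4.0 | 0.31 | 0.80 |
| 0.7 | 0.7×14 + 0.3×1 = 10.1 | 0.78 | 2.02 | 0.7×7 + 0.3×1 = 5.2 | 0.40 | 1.04 |

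- At f = 0.5 the sign turns on whether non-hormonal failure is above or below 7.5.
- With non-hormonal failure at 5, a real doubling with f = 0.3 gives 0.98, while no modulator effect with f = 0.7 gives 1.04. The method mix alone can reverse the ordering.
- If every method starts at 5 and pills double to 10, oral versus other hormonal is 10/5 = 2.0. The pooled RR is (10f + 5(1 − f))/5 = 1.30, 1.50 or 1.70 for f = 0.3, 0.5 or 0.7: diluted, but in the hypothesised direction.

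**2. The contrasts that are needed**

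On the first set of rates, oral versus other hormonal on modulators is 14/1 = 14. Off modulators it is already 7/1 = 7. The first ratio answers the hypothesis as written. Only the comparison of the two, 14/7 = 2, or oral on versus off modulators, 14/7 = 2, speaks to a modulator effect.

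**3. Precision of those contrasts**

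Section 7.7 gives 575 women, about half on hormonal methods. Assume half of those use pills: 575 × 0.5 × 0.5 ≈ 144 women per hormonal group. Assume also that 30% spend 3 years on modulators (144 × 0.3 × 3 ≈ 130 woman-years per group) and that each group has 720 woman-years off modulators.

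Expected events:
- On modulators: oral 130 × 0.14 = 18.2; non-oral 130 × 0.01 = 1.3.
- Off modulators: oral 720 × 0.07 = 50.4; non-oral 720 × 0.01 = 7.2.

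SE of a log ratio = √(sum of 1/events):
- Oral versus non-oral on modulators: √(1/18.2 + 1/1.3) = 0.91. For a true ratio of 14, the 95% CI is about 2.4 to 83.
- Oral on versus off modulators: √(1/18.2 + 1/50.4) = 0.27. For a true ratio of 2, about 1.2 to 3.4.
- Method-by-modulator ratio: √(1/18.2 + 1/1.3 + 1/50.4 + 1/7.2) = 0.99. For a true ratio of 2, about 0.3 to 14.
- The same with modulator time doubled (36.4 and 2.6 events): √(1/36.4 + 1/2.6 + 1/50.4 + 1/7.2) = 0.76, about 0.45 to 8.8.

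With one or two expected events in a cell these intervals are rough, but the ranking of the contrasts is clear.

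**The case against.** - **The pooled contrast looks deliberate.** Research question 6 and the objective agree, and section 2.0 speaks of hormonal contraception in general before narrowing to pills. This stands as a reason to keep the contrast as a description and to amend the research question together with the objective. It does not make the contrast a test of the section 3.0 hypothesis.
- **The data allow the right analysis, and the plan is still open.** Table 10 collects the necessary items, and sections 6.0 and 7.7 say that the analysis plan will be refined during the pilot. A reader might infer that the study cannot address the hypothesis at all. That goes too far: the gap is in the objective and the planned analysis, not in the data. The general promise to refine does not supply the contrast.
- **The hypothesis makes no claim about on versus off modulators.** A reader might infer that section 3.0 says modulators weaken pills, so that only an interaction test will do. Its wording compares oral with other hormonal methods during modulator use, and a comparison within modulator-exposed time tests that directly. The modulator effect is the section 2.0 concern and needs the further contrasts.
- **Reassurance is not the inevitable error.** A reader might infer that the plan will make failing pills look protective. That depends on a high non-hormonal failure rate, which the documents do not give. They also do not say whether sterilisation, recorded in the survey, counts as non-hormonal. With a rate of 5 the pooled RR is 1.5.
- **An interaction will be imprecise.** This is correct, and is why it should not be the only test.

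**Conclusion.** The mismatch holds. Sections 2.0 (research question 6) and 4.2 specify a contrast that tests neither the section 3.0 hypothesis nor the section 2.0 concern about pills, and section 9.3, Table 5 and section 8.1 do not repair it. Under the assumed rates, the same doubling of pill failure gives a pooled RR of 0.58 or 1.5 depending only on the non-hormonal rate. These figures illustrate non-identification; they do not predict the result. That the pooled contrast mixes pill share, ordinary method differences and modulator effect does not rest on the particular rates.

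This is one of eight secondary objectives and the primary exacerbation analysis is unaffected. The change should be made, but it does not threaten the study as a whole.

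**What to change.** Align research question 6 (section 2.0), the hypothesis (section 3.0) and the objective (section 4.2), and state whether comparators must also be on modulators. Add a pregnancy outcome to Table 5, and to section 9.3 a model of unintended pregnancy per woman-year by method (oral hormonal, non-oral hormonal, non-hormonal) and time-varying modulator use. State that pregnancy is the event in this model, whatever the censoring rule for the primary analysis. Then:

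1. Test the written hypothesis with oral versus non-oral hormonal methods in modulator-exposed time.
2. Because methods may differ without modulators, also report oral on versus off modulators and the method-by-modulator ratio, with confidence intervals, as the evidence on a modulator effect.
3. Keep hormonal versus non-hormonal as descriptive, and define which methods count as non-hormonal.

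The cost is mostly wording and a little more analysis, since the survey already collects method, modulator and pregnancy-intention data. One real addition is a rule, fixed in advance, for assigning a pregnancy to a method and to modulator status when only ages or calendar years are reported, with a sensitivity analysis for ambiguous cases. The interaction will probably be imprecise (log-ratio SE about 0.8 to 1.0 under the assumed exposure), so the plan should say that a non-significant interaction is not evidence that pills keep their effectiveness on modulators.
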